### **2.4       Determination of sample size**

It is anticipated that approximately 210 subjects will be randomized in a 1:1:1 ratio to the CZP 200mg Q2W, CZP 200mg Q4W, and PBO treatment groups. The primary efficacy analysis is based on the proportion of subjects who do not experience a flare during Part B of the study. The proportion of subjects who do not experience a flare during Part B is assumed to be 80%, 75%, and 45% for the CZP 200mg Q2W, CZP 200mg Q4W, and PBO treatment groups, respectively. Given these assumptions, a sample size of 70 subjects per group provides 98% power to detect a significant difference between the CZP 200mg Q2W dose and PBO and 94% power to detect a significant difference between the CZP 200mg Q4W dose and PBO using a 2-sided significance level of 0.05.

Given that subjects enter Part B only if they have achieved sustained remission in Part A, it is necessary to estimate the number of subjects needed to enroll in Part A. It is assumed that approximately 28% of subjects enrolled in Part A will achieve sustained remission and qualify for Part B. This means that about 750 subjects will be enrolled in Part A in order to have 210 subjects who are randomized into Part B.

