### **3.3 Analysis time points**

The analysis time point of interest for Part A is Week 48. Additional time points of interest for Part A are the Screening Visit, Week 0, Week 2, Week 4, Week 12, Week 24, Week 32 and

Week 36. For subjects who withdraw early during Part A, data recorded at the Withdrawal Visit will be assigned to what would have been the next scheduled visit for the particular assessment that is being summarized, unless otherwise specified. These data will be included in the summaries of the assigned visit and the “Early Withdrawal” visit if applicable. If a subject withdraws early during Part A but does not have a Withdrawal Visit in Part A, safety and efficacy data recorded at either the date of the last scheduled or unscheduled visit during the treatment Period, whichever is later, will be included in summaries of “Early Withdrawal” visit. Only post Part A Baseline assessments will be included in the “Early Withdrawal” visit.

The analysis time point of interest for Part B is Week 96. Additional time points of interest for Part B are Week 48, Week 50, Week 52, Week 54, Week 56, Week 58, Week 60, Week 62, Week 64, Week 66, Week 68, Week 70, Week 72, Week 74, Week 76, Week 78, Week 80, Week 82, Week 84, Week 86, Week 88, Week 90, Week 92 and Week 94. For subjects who complete Week 96, safety and efficacy data recorded at a Week 96/withdrawal Visit will be included in summaries of the Week 96 visit and the “Last/Withdrawal” visit if applicable. For subjects who withdraw from Part B prior to Week 96, data recorded at the Withdrawal Visit will be assigned to what would have been the next scheduled visit for the particular assessment that is being summarized, unless otherwise specified. These data will be included in the summaries of the assigned visit and the “Last/Withdrawal Visit” if applicable. If a subject withdraws early during Part B but does not have a Week 96/withdrawal Visit, then safety and efficacy data recorded at either the date of the last scheduled or unscheduled visit during the treatment Period, whichever is later, will be included in summaries “Last/Withdrawal Visit”. For subjects experiencing a flare, the last visit prior to escape medication (e.g. Escape Week 0) will be included in the summaries of the “Last/Withdrawal Visit”. Only post Part B Baseline assessments will be included in the “Last/Withdrawal Visit”.

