### 3.10 Changes to protocol-defined analyses

The SAP specifies which Baseline value is applicable for each analysis. The Flare Baseline is defined as the latest measurement for that subject up to and including the day of administration of first escape treatment in Part B instead of the visit in which the flare occurred.

In addition to the protocol, a modified version for ASDAS-MI is added for sensitivity analysis of ASDAS-MI.

Furthermore, analysis for IBD-Q response and IBD-Q remission using Part A Baseline and Part B Baseline as a reference and SF-36 PCS response and SF-36 MCS response using Part A Baseline as a reference are added.

Exploratory statistical comparisons for WPS will be based on MMRM instead of nonparametric bootstrap-t method.

ASDAS-Moderate Disease changed to ASDAS-Low Disease activity (Machado et al. 2018).  
LOCF analysis are removed from Part B efficacy tables.

MMRM will be used instead of ANCOVA based on LOCF for

- Total spinal pain
- Nocturnal spinal pain
- PtGADA
- Average of Questions 5 and 6 of the BASDAI concerning morning stiffness
- SF-36 PCS, MCS, and physical function domain
- Fatigue NRS
- ASQoL.

The primary purpose of the study is to evaluate treatment options of axSpA patients after being in sustained remission. Hence, one of the objectives is to evaluate the PK and immunogenicity of these patients. The CZP plasma concentration and ADAb titer of the patients that did not reach sustained remission are therefore not analysed, the Pharmacokinetic Set A (PKSA) as described in the protocol has been removed from the SAP.

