The LOCF imputation will be done whether the data is missing, the subject discontinued prior to the time point assessed, or the data is considered missing due to start of escape treatment.

Unless otherwise stated, the following guidelines apply for the LOCF analyses:

- For missing post-baseline Part A assessments, only carry forward earlier Part A post-Baseline values. Screening and Part A Baseline values do not get carried forward to the Part A post-Baseline visits.
- For missing post Week 48 Part B assessments,
  - if the subject did not experience a flare in Part B, only carry forward earlier Part B post-Week 48 values,
  - if the subject experienced a flare in Part B, the assessment at Escape week 0 will be treated as the last assessment in Part B prior to escape treatment. For any missing post 48 Part B assessments up to the week of flare (the later visit if flare was based on 2 visits), carry forward earlier Part B post-Week 48 values. Assessments whilst on escape treatment are not to be used, therefore the assessment at Escape week 0 will be carried forward for all subsequent visits until Week 96. E.g if the subject experienced a flare at week 72 then the Escape Week 0 assessment will be carried forward for the assessments after week 72 in Part B (76, 80, 84, 88, 92 and 96)

- Week 48 values do not get carried forward to the Part B post-Baseline visits.
- Assessments during escape treatment will not be carried forward.
- The following continuous endpoints in Part B will be compared between treatment groups using a mixed model for repeated measures (MMRM). The pattern of missingness for these variables is assumed to be MAR. Subjects who enter Part B will have already demonstrated sustained remission through 48 weeks on CZP 200mg Q2W. Many of these subjects will be randomized to receive placebo and will, therefore, be more likely to experience a flare. Post-flare data for subjects experiencing a flare (in any treatment group) will be treated as missing for the MMRM analysis. It is further assumed that most subjects who discontinue at this late stage in the study (i.e. during Part B) will do so as a result of reduced efficacy. Therefore, missing efficacy data due to either flare or study treatment discontinuation should be dependent on the observed efficacy scores, but independent of unobserved data. For the following continuous endpoints in Part B, imputation of missing data will be performed using the MMRM approach:
  - ASDAS
  - BASDAI

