### **8.2.2.2 Continuous secondary efficacy variables**

Summary statistics of observed and change from Part B Baseline to Week 96 values for ASDAS, BASDAI, BASFI, and BASMI will be presented by treatment group. These summary statistics will be repeated for Part A Baseline.

The changes from Part B Baseline to Week 96 in ASDAS, BASDAI, BASFI and BASMI will be compared between treatment groups using a MMRM. The pattern of missingness for these variables is assumed to be MAR. Post-flare data for subjects experiencing a flare (in any treatment group) will be treated as missing in the MMRM analysis. The MMRM methods will be applied to all observed change from Part B Baseline data obtained from Week 48 up to Week 96. The model will include Part B Baseline score as a fixed-effect covariate, treatment group, region, mNY classification, and visit as fixed-effect categorical factors, and Part B Baseline-by-visit and treatment group-by-visit as interaction terms. The multiple visits for each subject will be incorporated as repeated measures (fixed term) within each subject (random term). An unstructured covariance matrix will be used and visit will be treated as a categorical predictor. An unstructured correlation pattern will be used to estimate the variance-covariance of the within-subject repeated measures. Summary tables will present the adjusted means for PBO and the CZP doses, the respective differences to PBO, the corresponding p-values, and 95% CIs.

The comparison between treatment groups using MMRM will be repeated for Part A Baseline with Part A Baseline score as a fixed-effect covariate, treatment group, region, mNY classification, and visit as fixed-effect categorical factors, and Part A Baseline-by-visit and treatment group-by-visit as interaction terms.

Summary statistics of observed and change from Part B Baseline to Week 96 values for SIJ SPARCC and Spine ASspiMRI-a in the Berlin modification scores will be presented by treatment group. These summaries will be based on observed case data.

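### The missing-at-random argument for the Part B MMRMs does not carry over from ASDAS to BASFI, BASMI and the other scores, and the pre-escape visit has no defined place in them

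*SAP*

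**What the plan says.** SAP 8.2.2.2 compares change in ASDAS, BASDAI, BASFI and BASMI between arms by MMRM. The terms are the outcome's own baseline, treatment, region, mNY classification, visit and two interactions. Its exclusion rule is: "Post-flare data for subjects experiencing a flare (in any treatment group) will be treated as missing in the MMRM analysis". Section 8.3.2.3 repeats the model by visit, and 8.3.2.5 (fatigue), 8.3.2.7 (ASQoL), 8.3.2.8 (WPS) and 8.3.2.11 (SF-36) refer to it. None of the non-ASDAS models has an ASDAS term.

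The justification in 4.2 is that data missing because of flare or discontinuation "should be dependent on the observed efficacy scores, but independent of unobserved data".

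Under 3.2.22, flare is ASDAS of at least 2.1 at two consecutive visits or above 3.5 once. Withdrawal, two missed ASDAS visits and wrongly triggered escape are also counted.

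Escape Week 0 is normally 2 weeks after the flare-defining assessment (2.3.3). Flare Baseline includes values up to and including the day of the first escape dose (3.4). The LOCF rules in 4.2 say that "the assessment at Escape week 0 will be treated as the last assessment in Part B prior to escape treatment". However, 3.10 records that "LOCF analysis are removed from Part B efficacy tables". Section 3.3 says that, for flared subjects, "the last visit prior to escape medication (e.g. Escape Week 0) will be included in the summaries of the" Last/Withdrawal Visit, and it assigns that value to no scheduled Part B visit.

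**The concern.** An MMRM gives valid estimates under MAR only if the variables that drive missingness are in the model. For BASFI, BASMI and the quality-of-life scores, values disappear because another, correlated variable crossed a threshold, and the model never sees that variable. A subject whose ASDAS has just met the flare rule is then projected to Week 96 from an outcome history that only partly reflects the relapse.

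The Escape Week 0 value would help, since it is taken before re-treatment and still reflects the randomized arm. The SAP does not say whether it counts as post-flare for the MMRM, and no current rule places it on a scheduled visit.

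Both problems fall mostly on placebo. At stake is the estimated effect of withdrawing CZP on function, mobility and quality of life, which would look milder than it is.

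**Working it through.** **1. The SAP's planning figures.** Section 2.4 gives the rates for full dose, half dose and PBO: "The proportion of subjects who do not experience a flare during Part B is assumed to be 80%, 75%, and 45" per cent. It adds that "a sample size of 70 subjects per group provides 98% power to detect a significant difference between the CZP 200mg Q2W dose and PBO". For half dose against PBO the figure given is 94%, also at a two-sided 0.05 level. The normal-approximation power is Φ[(d − 1.96·SE0)/SE1], with SE0 = √(2·p̄(1−p̄)/n) and SE1 = √((p1(1−p1)+p2(1−p2))/n).

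- 80% vs 45%: SE0 = 0.0818, SE1 = 0.0763; (0.35 − 0.1604)/0.0763 = 2.485, so 99.4%. With a continuity correction of 1/70 it is 98.9%, and with Fisher's test 98.9%.
- 75% vs 45%: SE0 = 0.0828, SE1 = 0.0788; (0.30 − 0.1623)/0.0788 = 1.747, so 96.0%. With the correction it is 94.1%, and with Fisher's test 94.0%.

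The stated 98% and 94% are consistent with a corrected or exact test, so these rates are a fair basis. The SAP gives no figure for the MMRMs.

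**2. Expected loss.** Subjects counted as flared: PBO 70 × 0.55 = 38.5; half dose 70 × 0.25 = 17.5; full dose 70 × 0.20 = 14.

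**3. Why MAR holds for one model and not the others.** Let A be ASDAS, Y another outcome and R the indicator that Y is observed. R is mainly a function of past observed A. In the A model, R depends on observed data, so MAR holds. In the Y-only model, MAR needs P(R | Y observed, Y missing) = P(R | Y observed). If A predicts future Y beyond Y's own history, this fails. BASDAI is a partial case because ASDAS uses its questions 2, 3 and 6.

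**4. Where the SAP starts post-flare.**

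| Section | Starting point |
|---|---|
| 3.2.29 medications | date of flare |
| 10.2 adverse events; 10.3 laboratory data | start of escape therapy |
| 8.3.2.9 uveitis, IBD and psoriasis events | counted up to Escape Week 0 |
| 4.2 LOCF rules | Escape Week 0 is still Part B |
| 8.2.2.2 MMRM | not stated |

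Section 3.3 maps a withdrawer's final visit to the next scheduled visit but gives no such mapping for an escaper.

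**5. First simulation.** It used 6,000 subjects per arm, 12 four-weekly visits, the ASDAS flare thresholds, and flare rates calibrated to 55% and 20% (achieved 54–56% and 19–20%). Values after the flare visit were deleted. Estimation was by maximum likelihood with unstructured covariance. The target is the Week 96 PBO minus full-dose mean difference had escape not started. Correlation of Y with ASDAS is assumed.

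| Correlation | True difference | MMRM as planned | One more pre-escape value | Joint with ASDAS |
|---|---|---|---|---|
| 0.67 | 0.851 | 0.753 (−12%) | 0.779 (−8%) | 0.865 (+2%) |
| 0.49 | 0.862 | 0.733 (−15%) | 0.772 (−10%) | 0.851 (−1%) |
| 0.28 | 0.431 | 0.363 (−16%) | 0.385 (−11%) | 0.439 (+2%) |
| 0.84 | 1.367 | 1.200 (−12%) | 1.253 (−8%) | 1.376 (+1%) |
| 0.68 | 1.434 | 1.161 (−19%) | 1.246 (−13%) | 1.437 (0%) |
| 0.40 | 0.688 | 0.566 (−18%) | 0.596 (−13%) | 0.729 (+6%) |

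The MMRM of ASDAS itself was within −1% to +1% throughout. The extra pre-escape value closes about a quarter to a third of the gap; in row 1, (0.779 − 0.753)/(0.851 − 0.753) = 27%.

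**6. Second simulation.** It used 40,000 subjects per arm. Relapse is a lasting shift (mean latent ASDAS rise 1.9), and Y is proportional to latent activity with independent noise of SD 0.5, 0.8 or 1.2. With 4-weekly visits the planned MMRM was off by −12%, −27% and −37%. With Escape Week 0 mapped to the next visit the errors were +6%, −9% and −21%. With ASDAS as auxiliary they were +16%, +10% and +5%.

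**The case against.** Several stronger readings are tempting, and the SAP does not support them.

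- *All Part B MMRMs are biased.* The ASDAS model is not, in simulation. Flare there depends on observed ASDAS, apart from triggers outside the model such as an unscheduled assessment.
- *The SAP discards Escape Week 0.* It never says so. Much of the SAP draws the line at the start of escape treatment. Omission is the natural reading of 3.3 and 8.2.2.2 together, but what can be shown is an undefined term and a missing visit mapping.
- *The difference could be halved.* Errors of −36% to −50% arise in the second simulation only if outcomes are measured every 12 weeks. The example in 4.2 lists the assessments after a Week 72 flare as Weeks 76, 80, 84, 88, 92 and 96. That is not a schedule per variable, but it points to 4-weekly.
- *Flared subjects are projected largely from subjects in remission.* The flare visit itself stays in the model. In row 1 above, the observed-case difference was 0.532, so the MMRM recovers (0.753 − 0.532)/(0.851 − 0.532) = 69% of the shortfall.
- *These are the only model-based results.* SF-36 PCS and MCS response (8.3.2.11) and the ASAS responses (8.2.2.3, 8.3.2.2) have logistic models with NRI, which do not rest on MAR. Nocturnal pain is named for MMRM in 3.10 and 4.2 but is only descriptive in 8.3.2.12, so it is left out here.

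Two further points stand. The 45% and 80% rates also count withdrawals and missed visits, whereas the simulations attribute every flare to ASDAS; this overstates the ASDAS-driven loss. Worsening at Escape Week 0 also remains visible in the Last/Withdrawal summaries.

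None of this rescues the MAR rationale for the non-ASDAS models. The sensitivity analyses in 8.1.3 and 8.2.2.1 cover flare and time to flare only.

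**Conclusion.** The point holds for the Part B MMRMs of BASFI, BASMI, ASQoL, SF-36, fatigue, WPS and, in part, BASDAI. Leaving ASDAS out is the main cause; the unplaced Escape Week 0 value is a smaller one. The likely direction is an understated Week 96 difference between full-dose CZP and PBO. The size is roughly 12% to 19% under the first set of assumptions, and up to 37% with noisier outcomes.

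These sizes rest on assumed correlations and noise, 4-weekly measurement, persistence of relapse without escape, and an outcome that moves with disease activity (untested for BASMI). Half dose against PBO was not simulated; the expected imbalance there (25% against 55%) runs the same way.

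The primary endpoint and time to flare are untouched, and 8.2.2 and 8.3.2 label the p-values nominal. This is a worthwhile, inexpensive improvement to secondary and other analyses; it does not threaten the trial's main conclusion.

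**What to change.** 1. In 4.2, 8.2.2.2 and 8.3.2.3, define post-flare data for the MMRM as assessments after the first escape dose. State that the Escape Week 0 assessment, where taken before that dose, enters as the next scheduled Part B visit for that variable, as 3.3 already does for withdrawals.
2. Limit the MAR rationale in 4.2 to ASDAS. For the other continuous outcomes, add a sensitivity analysis by multiple imputation or a joint model, with the ASDAS history up to flare or Escape Week 0 as auxiliary, followed by the same MMRM.

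Change 2 addresses the main cause. It belongs as a sensitivity analysis because in the second simulation it overshot by 5% to 16%, and at the lowest noise level by more than the planned model fell short.

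The cost is SAP wording and some programming; Escape Week 0 is already an analysis visit and feeds Flare Baseline. The one drawback is timing: after a Week 72 flare, a value from about Week 74 would stand for Week 76.

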### **3.2.22.4 Referenced based multiple imputation of ASDAS**

Missing data for the ASDAS scores at any visit in Part B up until Week 92 because of subject premature withdrawal, of subject experiencing a flare or of missing assessment at a given visit will be handled at each visit via reference based multiple imputation as described below:

This procedure will use an imputation model developed based on data from the PBO group only (Mallinckrodt, 2013). The reference-based multiple imputation assumes that the statistical behavior of the CZP and PBO-treated subjects after discontinuing study medication becomes that of the PBO-treated subjects. Data collected after discontinuation of the double-blind study treatment for both the CZP and PBO groups will be considered missing. Multiple imputations are used to replace missing outcomes for CZP- and PBO-treated subjects who discontinued using multiple draws from the posterior predictive distribution estimated from the PBO arm.

For subjects with a non-monotone (intermittent) missing pattern, Markov chain Monte Carlo (MCMC) will be used to impute their missing intermittent ASDAS scores by randomized treatment, geographic region and mNY classification. This will be done only once for each subject in order to provide a dataset with monotone missing (seed will be 221).

Data are processed sequentially by repeatedly calling SAS® PROC MI to impute missing outcome data at visits  $t=1, \dots, T$ , where  $t=1$  is Week 48 and  $t=T$  is Week 92

*Initialization.* Set  $t=1$  (Part B Baseline visit)

*Iteration.* Set  $t=t+1$ . Create a data set combining records from CZP- and PBO-treated subjects with columns for covariates (geographic region and mNY classification) and outcomes at visits 1 to  $t$ . Outcomes for all CZP-treated subjects are set to missing at visit  $t$  and set to observed or previously imputed values at visits 1 to  $t-1$ . Outcomes for PBO-treated subjects are set to observed at visit  $t$  or observed or previously imputed values at visits 1 to  $t-1$ .

*Imputation.* Run MCMC to impute missing values for visit  $t$  using previous outcomes for visits 1 to  $t-1$ , geographic region and mNY classification. Note that only PBO data will be used to estimate the imputation model since no outcome is available for drug-treated subjects at visit  $t$ .

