### **3.4 Definition of Baseline values**

The study baseline value for a subject noted “Part A Baseline” will be defined as the latest measurement for that subject up to and including the day of administration of first study medication in Part A, unless otherwise stated. If a Part A Baseline measurement is missing or not collected, and a Screening value is available, the Screening value will be utilized as Part A Baseline instead. If no measurement is available prior to receiving study medication in Part A, the Part A Baseline value is treated as missing.

For subjects randomized into Part B, a “Part B Baseline” will be defined as the latest measurement for that subject up to and including the day of randomization, unless otherwise stated. If a Part B Baseline measurement is missing or not collected, and a post-Baseline Part A value is available, the post-Baseline Part A value will be utilized as Part B Baseline instead. If no post-Baseline Part A measurement is available prior to randomization, the Part B Baseline value is treated as missing.

For subjects experiencing a flare in Part B, a “Flare Baseline” will be defined as the latest measurement for that subject up to and including the day of administration of first escape treatment in Part B, unless otherwise stated. If a Flare Baseline measurement is missing or not collected, and a post-Baseline Part B value is available, the post-Baseline Part B value will be utilized as Flare Baseline instead. If no post-Baseline Part B measurement is available prior to receiving study medication in Escape Part, the Flare Baseline value is treated as missing. If a subject does not receive study medication in Escape Part, the last available post-Baseline Part B measurement will be used as Flare Baseline.

For each baseline definition, if there is evidence that measurements taken on the same day as administration of first study medication (in Part A/Part B) or first escape treatment (for subjects experiencing a flare in Part B) were actually taken after this administration, then only values strictly prior to that date (including screening assessment visits if appropriate) will be used for that subject. When the date of first dose is derived, it should be based on the first injection of study treatment, regardless of whether it is an active treatment.

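### The MMRM of change from Part B Baseline in SAP 8.2.2.2 takes in the baseline visit as a response, so its unstructured covariance is singular or nearly so

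*SAP*

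**What the plan says.** Section 8.2.2.2 compares the arms on change from Part B Baseline to Week 96 in ASDAS, BASDAI, BASFI and BASMI. On the data window it says: "The MMRM methods will be applied to all observed change from Part B Baseline data obtained from Week 48 up to Week 96". On the covariance it says: "An unstructured covariance matrix will be used and visit will be treated as a categorical predictor". Treatment and the baseline score each interact with visit. Region and mNY classification enter as main effects only, so each has one coefficient for all visits.

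Section 3.4 has Part B Baseline "defined as the latest measurement for that subject up to and including the day of randomization, unless otherwise stated". Three other places show how Week 48 is regarded:

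- Section 3.2.22.4 starts its visit sequence at Week 48 and calls that the "Part B Baseline visit".
- Section 4.2 keeps Week 48 apart from later visits: "Week 48 values do not get carried forward to the Part B post-Baseline visits".
- Section 3.3 nevertheless lists it as a Part B time point: "Additional time points of interest for Part B are Week 48, Week 50, Week 52".

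Section 8.2.2.2 gives no alternative covariance. Section 3.2.22.3 does give one (variance components or first-order autoregressive), but for the model that imputes ASDAS in a flare sensitivity analysis.

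**The concern.** If the baseline is the Week 48 value, the Week 48 change is that value minus itself. A visit whose response is zero for everyone has no variance and no covariance with any other visit. An unstructured matrix that includes it cannot be positive definite, so the model has no maximum-likelihood solution as written.

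The region and mNY adjustment suffers too. Week 48 carries effectively unlimited weight and shows no region or mNY effect, and the same coefficients must serve every later visit. At stake is whether the prespecified model for four secondary variables can be run as described, and whether its covariate adjustment does anything.

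The log for SAP Amendment 2 suggests how this arose: the model moved from change from Part A Baseline to change from Part B Baseline, and the window stayed the same. The point itself rests on the current text alone.

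**Working it through.** The SAP states no figure for this model, so there is none to reproduce.

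**Algebra.** Let B be a subject's Part B Baseline and Y(t) the score at visit t. The response is D(t) = Y(t) - B. With B = Y(48), D(48) = 0. The model is

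D(t) = visit(t) + treatment(t) + b(t) x B + region + mNY + e(t), with e having an unstructured covariance.

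Setting the Week 48 visit, treatment and slope terms to zero, and region and mNY to zero, leaves a Week 48 residual of exactly 0 for every subject. The Week 48 variance s2 then adds -(n/2) x ln(s2) to the log-likelihood, which grows without limit as s2 goes to 0.

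**Simulated fits.** The assumptions are not from the SAP: 210 subjects, 70 per arm; visits at Weeks 48, 60, 72, 84 and 96; invented means and SDs; data missing after an ASDAS of 2.1 or more; about 3% dropout per visit. Estimation was by maximum likelihood (EM).

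As written, with Week 48 as a response:

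| Step | Log-likelihood | Week 48 variance | Condition number |
|---|---|---|---|
| 1 | -725.6 | 1.6e-3 | 4.7e2 |
| 2 | -67.4 | 9.4e-7 | 9.4e5 |
| 3 | 718.3 | 1.140e-9 | 8.0e8 |
| 4 | 1423.7 | 1.556e-12 | 5.9e11 |
| 5 | 2116.3 | 2.1e-15 | 4.3e14 |

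Each log-likelihood is evaluated at the variance from the step before. From step 4 to step 5 the formula predicts a rise of (210/2) x ln(1.140e-9 / 1.556e-12) = 105 x 6.597 = 692.7. The observed rise is 2116.3 - 1423.7 = 692.6, equal to within rounding. The growth therefore comes from the Week 48 variance collapsing.

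Comparison of fits:

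| Fit | Condition number | Largest region/mNY coefficient (size) | Week 96 Q2W minus PBO (SE) |
|---|---|---|---|
| As written, last step | 4.3e14 | 0.0000 | -0.559 (0.099) |
| Visits after Week 48 only | 6.8 | 0.073 | -0.569 (0.099) |
| 1 of 210 with non-zero Week 48 change | 3,830 | 0.003 | -0.559 (0.099) |
| 3 of 210 | 1,300 | 0.006 | -0.556 (0.099) |
| 10 of 210 | 578 | 0.011 | -0.555 (0.099) |
| Change from Part A Baseline, Week 48 kept | 25 | 0.084 | -0.561 (0.100) |

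Without Week 48 the fit settles by about ten iterations (log-likelihood -544.43, smallest eigenvalue 0.129). The rows with 1, 3 or 10 exceptions represent subjects whose baseline predates Week 48. Those fits converge, but with a Week 48 variance of only 2e-4 to 2e-3 and with region and mNY still pulled towards zero.

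The Week 96 contrast differs by 0.5691 - 0.5586 = 0.0105 between the first two fits, about 0.1 of its standard error (0.0105 / 0.0994).

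**The case against.** The best defence is that any programmer would drop the baseline visit. Section 4.2 already separates Week 48 from the post-baseline visits, the choice does not depend on the data, and the simulated treatment contrast barely moves. That limits the consequence, but the current sentence still names Week 48 as the start of the window.

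It is also fair that zero for everyone is not guaranteed. Section 3.4 falls back to an earlier value when same-day measurements were evidently taken after dosing. Such exceptions turn an impossible fit into a badly conditioned one.

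Some stronger readings are not supported:

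- **Every MMRM in Sections 8.3.2.3 to 8.3.2.11 fails.** The Week 48 window is stated only in 8.2.2.2. Section 8.3.2.3 speaks of each visit in Part B, and Section 2.2.1.3.2 confines those variables to visits after the first Part B dose. Sections 8.3.2.6, 8.3.2.9 and 8.3.2.10 contain no MMRM.
- **These are key secondary tests.** The SAP has no such tier. Section 8.2.2 calls the p-values nominal.
- **The team would have to improvise after unblinding.** A zero response at baseline would show in any programming run with dummy treatment codes.
- **The Part A Baseline repeat is broken, or should swap its covariate for the Part B Baseline score.** The Week 48 change from Part A Baseline varies between subjects, and that fit is regular. The main model already adjusts for Part B Baseline. A swap can lose precision. Assume SDs of 0.8 (Part A Baseline, A), 0.25 (Part B Baseline, B) and 0.6 (outcome, Y), with correlations AY 0.2, BY 0.4 and AB 0.2. The residual variance of Y - A given A is 0.36 x (1 - 0.04) = 0.35. Given B alone it is 0.808 - 0.02^2 / 0.0625 = 0.80.

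**Conclusion.** The point holds for the MMRM of change from Part B Baseline in Section 8.2.2.2. As written, the unstructured model is singular if every subject's baseline is the Week 48 value, and severely ill-conditioned if a few subjects have an earlier one. The section offers no fallback. The region and mNY adjustment is lost or nearly lost in either case.

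This is a specification that cannot be run as stated, with no large bias shown. It touches four secondary variables with nominal p-values. The logistic regression for the primary variable in Section 8.1.1 does not use this model. The singularity follows from the SAP's own definitions. The sizes quoted for conditioning, coefficients and the Week 96 contrast rest on simulated data with assumed means, SDs, visits and dropout, and are illustrative.

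**What to change.** In Section 8.2.2.2, for change from Part B Baseline, limit the response to visits after Week 48 up to Week 96. Keep the Part B Baseline score and its interaction with visit as covariates.

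Add an ordered fallback covariance in case the unstructured fit does not converge, for example heterogeneous Toeplitz and then first-order autoregressive. A fallback alone would not be enough: with Week 48 kept, a structure with visit-specific variances still meets a zero variance, and one with a common variance is pulled down by the zeros.

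In Section 8.3.2.3, state that the Part B visits modelled are those after Week 48, since Section 3.3 lists Week 48 as a Part B time point. Leave the Part A Baseline repeat with its Part A Baseline covariate, and say explicitly whether Week 48 stays a response there.

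The cost is a few sentences in the SAP. No data collection, sample size or primary analysis changes.
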